7.1.1 Data collection, management, and analysis

Demographic background data and treatment history will be collected from interview and medical records at baseline.

Assessments will be made with established and well-validated rating scales and questionnaires in addition to one research interview that was developed by the principal investigator (PNISSI) (see list of all rating scales and questionnaires below). Sampling of biological materials will be done by a standard operating procedure (SOP) used for sampling for other current cohorts. We will also perform laboratory tests in a highly structured manner with well-validated methods in collaboration with researchers at Örebro University and Karolinska Institutet. Samples will be frozen and stored in Region Örebro County biobank (458) at -80 °C until analysis. All data collection forms will be stored at a safe place within Örebro hospital, Region Örebro County.

7.1.2. Rating scales and tests

If more than one clinician will assess the patients rating calibration training for obtaining agreement on scorings will be performed.

Due to the large data collection in combination with the severity of the disorder in these patients missing data will be unavoidable. We will try to avoid missing data by providing clarification if a patient cannot understand the meaning of a question. For each symptom rating scale the response rate is set at a minimum of 80 % of the questions. Isolated missing scores will be replaced with the individual mean.

Demographics

- Background data collection form
- Pans Data Collection Form provides information about inherited physical and psychiatric disorders within the family.

Diagnostic interviews

- Mini International Neuropsychiatric Interview (M.I.N.I. version 7) is a structured clinical interview for psychiatric disorders. In addition the childhood onset diagnoses from the M.I.N.I. kid version will be amended to the adult version of M.I.N.I. (66, 67)
- PsychoNeuroinflammatory Related Signs and Symptoms Inventory (PNISSI) in order to identify and measure symptoms related to neuro-inflammation and diagnose PANDAS and PANS (68)

Assessment of severity, improvement and quality of life

- Clinical Global Impression-Improvement scale (CGI-I) measures change of symptoms on a 7 point Likert scale. CGI-I will also be administered to the next-of-kin (69)
- Patient's Global Evaluation (PGE) provides a self-administered global measure of improvement on a 7 point Likert scale (70)
- Clinical Global Impression-Severity scale (CGI-S) provides a global measure of illness severity on a 7 point Likert scale (69)
- Global Assessment of Functioning (GAF) measures general disability and symptom burden (71)
- Personal and Social Performance Scale (PSP) (72). The PSP is a 100-point single-item rating scale, subdivided into 10 equal intervals. The ratings are based mainly on the assessment of patient's functioning in four main areas: 1) socially useful activities; 2) personal and social relationships; 3) self-care; and 4) disturbing and aggressive behaviours.
- Level 1 Cross-cutting symptom measure of global symptom severity is a patient or informant rated measure included in the DSM-5, which assesses mental health domains that are important across psychiatric diagnoses. It includes 13 domains. We will use it with the clinician's assistance for adults (73)
- Brunnsviken Brief Quality of Life Inventory (BBQ) is a 12-item measurement of life satisfaction (74, 75)
- EuroQol Group EQ-5D™ (EQ-5D-5L) is an 5-item quality of life inventory (76)

Obsessive-Compulsive disorder

- Brief Obsessive Compulsive Scale (BOCS) maps self-reported symptoms and measures severity of obsessive-compulsive symptoms by a clinician (77)

- National Institute of Mental Health Global Obsessive Compulsive Scale (NIMH GOCS) is a global assessment of OCD severity (78)

Autism spectrum disorder

- Clinician-rated Severity of Autism Spectrum and Social Communication Disorder is a DSM-5 based measure for assessing severity of autism spectrum disorder (79)
- RAADS-R is a self-report to assess autistic symptoms. If the patient is unable to fill it out this can be done by a next-of-kin (80)

Schizophrenia spectrum disorder

- Clinician-rated Dimensions of Psychosis Symptom Severity is a DSM-5 based measure for assessing severity of a psychosis (79)
- Positive and Negative Syndrome Scale (PANSS) is a measure for psychotic symptoms in schizophrenia (81).

Catatonia

- Bush-Francis Catatonia Rating Scale (BFCR) is a 23 item measure for catatonic symptoms (82)

Anxiety and depression

- Hospital Anxiety and Depression Scale (HADS) is a combined brief self-report measure for anxiety and depressive symptoms (83)

Trauma

- The Children's Impact of Events Scale (CRIES-8) is an 8-item self-report to measure post-traumatic symptoms. In the present study it will be used in adults (84)

Personality syndrome

- The Personality Inventory for DSM-5 Brief Form is a brief self-report (79, 85)

Early onset psychiatric symptoms

- Five to fifteen-Brief (FTF-Brief) consists of 24 items representing 18 of the original 22 subdomains in the original Five to fifteen questionnaire for assessing childhood neurodevelopmental symptoms (86). The FTF-Brief has been validated by us to be used in retrospect in adults assessed in childhood for neurodevelopmental disorders, and reassessed in adulthood (87).

Cognitive tests

- Parts of Wechsler Intelligence Scale Revised (WAIS-III-R) and/or WISC-III; WAIS-III; D KEFS; Wechsler Memory Scale, and from PNISSI.
- Block design, digit span, letter number sequencing and digit symbol coding, visuospatial test
- Adult executive functioning inventory (ADEXI) is a 14 item self-report of working memory and impulsivity (88)

Motor skill test

- Nine hole peg test (89)
- Gross motor functioning (from PNISSI) (90)

Side-effects

- Safety and tolerability of rituximab measured in an interview (AAR).
- UKU side effect rating scale is a clinician-rated scale with 48 items (91).

In addition to UKU, adverse events will be checked with the following questions at each visit:

1. Have you noticed any new symptoms or problems since your last visit? If yes, which?
2. Do you gather these symptoms can be related to your rituximab treatment?
3. Have you noticed if any of your previous side effects have attenuated or increased? If yes, which ones?

Treatment satisfaction

- Client satisfaction questionnaire (CSQ-8) is an 8-item measurement that is designed to measure client satisfaction with services (92)

Other rating scales

- Bristol stool scale to evaluate the consistency of faeces and therefore obtaining a measure of transit through the gastrointestinal tract (93)

Physical examination

- General condition; blood pressure; heart rate; signs of joint inflammation; dermatological examination; height and weight
- Basic neurological examination

Video recording

Each patient will be video recorded at base line, week 12, 20 and 40 in order to enable blinded assessment by an independent rater, and for the patient's own evaluation.

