5.2 Outcomes

Primary outcome

The primary outcome measure is change in symptoms measured as change in PANSS score.

Secondary outcome

- Global improvement at week 20, according to a balanced assessment (mean value of three independent assessors: 1) The treating clinician, 2) The patient's self-assessment and 3) A next-of-kin) using the Clinical Global Impression-Improvement (CGI-I) scale (range 1-7; 1 representing "Very much improved").
- Change in Personal and Social Performance Scale (PCP) measuring overall disability
- Change from baseline up to week 20 of illness severity (CGI-S) assessed by the clinician
- Difference from baseline up to week 20 in inflammatory markers in blood (gene expression and proteins) in relationship to clinical response (CGI-I)
- Proportion of responders to treatment, i.e. rated as much or very much improved since baseline according to CGI-I assessed by three different informants: 1) The treating clinician, 2) The patient's self-assessment and 3) A next of kin. If the mean value of these three is below 2.5 then the patient will be regarded as a responder (representing much or very much improved since baseline).

- Safety and tolerability of rituximab during treatment for SSD measured with the questionnaire Any Adverse Reactions (AAR).

Other outcome measures

- B-cell depletion at week 5, and B-cell subpopulations at week 20 in relation to clinical response and baseline levels of B-cells
- Changes in cognitive functioning at 20 weeks:
 - Neuropsychological functioning assessed with e.g. visuospatial and executive tests
- Change from baseline on rating scales that measure psychiatric symptoms specific for each diagnosis (shown below) *during the past 2 weeks*
 - BOCS for measuring obsessive-compulsive symptoms
 - RAADS-R for measuring autistic symptoms
 - PANSS for measuring psychotic symptoms
 - BFCR to measure catatonic symptoms
 - HADS for measuring depressive and anxiety symptoms

Long-term outcomes

40 weeks follow-up:

Outcome measures for long term are identical to that used at 20 week.

Change in symptoms measured as change in PANSS score.

The secondary outcome measures are:

- Global improvement at week 20, according to a balanced assessment (mean value of three independent assessors: 1) The treating clinician, 2) The patient's self-assessment and 3) A next-of-kin) using the Clinical Global Impression-Improvement (CGI-I) scale (range 1-7; 1 representing "Very much improved").

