Participants with severe SSD may not be able to respond to all questions or fill out rating scales. However, we will then obtain independent information whether the patient is improved or not according to CGI-I and PANSS even though h/she may not be able to fill out rating scales. Thus our primary outcome measure can be used at all times regardless of the state of the patient.

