10.2 Statistical methods and analytical plan

10.2.1 Primary objective: Improvement reflected in change in PANSS score

To investigate whether markedly ill, treatment-resistant, psychiatric patients according to our inclusion/exclusion criteria are significantly improved after treatment with the immunomodulatory drug rituximab (as addition to the patients' standard treatment).

We will analyse the clinical data on a modified intention-to-treat (ITT) definition basis, i.e. including treatment dropouts who received at least one dose of rituximab as well as completers. In addition, a completer-only analysis will be performed. *The primary outcome* is change in PANSS score, assessed by a clinician.

Secondary outcomes: CGI-I score (range 1-7). All CGI-I ratings are performed by three independent raters (the patient, his or her next of kin and a clinician). The mean value of these three values will be used as the patients' scores. If one of the values is missing, the mean will be calculated using only two values.

One secondary outcome is binary: the proportion of responders to treatment at week 20 (and similarly at week 40). Treatment response is defined as a mean value below 2.5 on the CGI-I (calculated as above), which corresponds to the scale step descriptors "much improved" or "very much improved". Non-response is defined as a mean CGI-I value of 2.5 or higher.

The continuous secondary outcome variables at the 20-week and 40-week end points (CGI-S, PSP, and diagnosis specific rating scales) will be included in analysis of covariance (ANCOVA) models, controlling for baseline measures and demographic variables.

Side-effects will be closely monitored and types, frequency, severity and seriousness will be reported.

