10.2.3 Analyses of other clinical data related to clinical response

1. Change in PSP, measuring overall disability from baseline up to week 20.
2. Change from baseline up to week 20 of illness severity (CGI-S) assessed by the clinician.
3. Change from baseline on rating scales that measure psychiatric symptoms according to psychiatric rating scales.
4. To examine whether there is a change in cognition after treatment.

5. To investigate the patients' experiences of the novel treatment with a qualitative content analysis.

For results on the scales (PSP, CGI-S and psychiatric rating scales) the week 20 scores and the Δ -values (difference between scores at week 20 and baseline) will be tested by means of t-tests or Mann-Whitney tests, as applicable. They will also be included in an analysis of covariance (ANCOVA) model, controlling for baseline measures and other possible confounders, as demographic variables. The cognitive tests will be analysed with established methods, and possible changes will be compared before and after treatment. The qualitative content analysis does not involve quantitative statistics.

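### RAADS-R change scores can mix patient and next-of-kin reports, because nothing keeps or records the informant across visits

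*Combined protocol and SAP*

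**What the plan says.** Section 7.1.2, under autism spectrum disorder, introduces RAADS-R as a self-report and continues: "If the patient is unable to fill it out this can be done by a next-of-kin". Section 6.1 expects the situation to arise: "Participants with severe SSD may not be able to respond to all questions or fill out rating scales".

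Section 5.2 lists "RAADS-R for measuring autistic symptoms" among the other outcome measures, both for the main period and for long-term follow-up, as a change from baseline. The Synopsis gives the time points as week 20 and week 40. Table 1 places the psychiatric rating scales at screening and at weeks 20 and 40.

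The scores are analysed in two ways. In section 10.2.3 the week-20 scores and the differences from baseline are examined with t-tests or Mann-Whitney tests. In section 10.2.1 the continuous outcomes, including the diagnosis-specific scales, "will be included in analysis of covariance (ANCOVA) models, controlling for baseline measures and demographic variables". Section 10.2.4 carries the same methods to week 40.

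**The concern.** A change score means what it should only if both scores come from the same source. The proxy option is tied to the patient's inability. Read literally, it lapses when the patient becomes able and opens when the patient becomes unable. A patient represented by a next of kin at baseline who answers personally at week 20 contributes a difference that contains any systematic gap between the two informants as well as any real change. In the ANCOVA, that patient's self-report is adjusted for another person's baseline score.

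Such a switch may go along with improvement or deterioration, so the informant gap need not behave like random noise. The trial has one arm, so no control group shares the shift and cancels it. If the informant is not recorded, the problem cannot be reliably detected or corrected later.

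**Working it through.** **Is the informant fixed anywhere?** The places that could do so are these:

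- Rater calibration (7.1.2) applies to clinicians only.
- The missing-data rule (7.1.2) requires 80 % of items and fills isolated gaps with the individual mean. It concerns missing items, not a change of respondent.
- The ANCOVA covariates in 10.2.1 are baseline measures and demographic variables. Section 10.2.3 allows other possible confounders but does not name informant.
- No section requires the RAADS-R respondent to be recorded or restricts change scores to pairs from one informant.
- For CGI-I, section 10.2.1 treats patient, next of kin and clinician as three separate raters and averages them. It gives no comparable treatment for RAADS-R.

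The gap is therefore real, and it reaches an analysed outcome.

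**How large could it be?** The plan gives no RAADS-R figure to reproduce: no SD, no score range, no patient-versus-kin difference. The article cited for RAADS-R has RAADS-14 in its title, so even the scale length is not clear. I therefore work in SDs of the change score, and both quantities below are assumptions.

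Let k be the net number of patients, of 12, whose informant changes in one direction, and d the systematic informant difference. With no true change:

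shift in mean change = k × d / 12

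- k = 2: 2 × 0.25 / 12 = 0.04 SD, up to 2 × 1.0 / 12 = 0.17 SD
- k = 4: 4 × 0.25 / 12 = 0.08 SD, up to 4 × 1.0 / 12 = 0.33 SD
- k = 6: 6 × 0.25 / 12 = 0.13 SD, up to 6 × 1.0 / 12 = 0.50 SD

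Section 10.2.3 does not say which groups its t-test compares. I took a one-sample test of the change (n = 12, two-sided 5 %, normal data, no true change, 200,000 simulated trials). It rejects in:

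| k | d = 0.5 SD | d = 1.0 SD |
|---|---|---|
| 2 | 5.3 % | 6.4 % |
| 4 | 7.4 % | 13.3 % |
| 6 | 11.2 % | 26.9 % |

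With two switches the effect is slight. It becomes material only if a third or more of the patients switch in the same direction and the informants differ clearly.

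**The case against.** Several stronger readings are tempting and do not stand.

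*That every patient who improves changes informant.* The text permits a next of kin to answer; it does not prescribe a fresh choice at each visit or a return to self-report. Patients can improve or worsen without crossing the threshold of being unable, and inability can have causes unrelated to response. Entry also limits inability at baseline: patients must be lucid and oriented at consent and able to make an informed decision, and staff clarify questions that are not understood. Section 6.1 nevertheless still expects some inability, so the possibility remains.

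*That the Level 1 cross-cutting measure has the same flaw.* Section 7.1.2 says it "is a patient or informant rated measure included in the DSM-5", but this describes the instrument. The same bullet says that the trial will use it with the clinician's help for adults, and all participants are adults. It is not a listed outcome, and Table 1 does not schedule it at week 40.

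*That the bias can be stated in scale points.* The documents give nothing to anchor such a figure. Switches in opposite directions would partly cancel, and the direction of the informant difference is unknown.

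It is also fair to say that section 7.1.2 includes a clinician-rated autism severity measure that is free of this problem, and that the open wording on confounders in 10.2.3 could accommodate informant. The first does not repair the RAADS-R change. The second helps only if someone records who answered.

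**Conclusion.** The point holds for RAADS-R only and is minor. The plan allows a change score built from two informants, and the switch may be linked to clinical change. Whether this happens, how often, and in which direction it would bias the result cannot be determined from the documents. The SD-based figures are illustrations that rest on assumed numbers of switches, all in one direction, and an assumed informant difference.

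The main conclusions of the trial are not at risk. PANSS is rated by a clinician, and responder status comes from CGI-I. RAADS-R is an other outcome in section 5.2, although section 10.2.1 groups the diagnosis-specific scales with the continuous secondary outcomes.

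**What to change.** In section 7.1.2, for RAADS-R:

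1. Record who completed the form at every visit.
2. If a next of kin completes it at baseline, the same next of kin completes it at weeks 20 and 40. If the patient becomes able, collect the self-report as well.
3. Where inability is foreseeable or doubtful, collect both reports at baseline, so that a patient who later becomes unable still has a matching pair.

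In sections 10.2.1 and 10.2.3, compute change within the same informant and keep every patient with a same-informant pair in the main analysis. Report the number of switches and add a sensitivity analysis that includes mixed-informant changes. Patients without a matching pair should not simply be dropped: that exclusion could itself be related to response, and there are only 12 patients.

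The cost is plan wording and at most one extra questionnaire per visit from a next of kin who already rates CGI-I.

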7.1.3 Biochemical and other measures

There is still insufficient knowledge concerning inflammatory/immunological mechanisms of psychiatric disorders. Therefore, in order to increase our understanding and to extend the interpretational potential of clinical findings from our exploratory study, we will assess relevant immunological parameters, autoimmune biomarkers, genetic SNPs, etcetera. Additionally, we will apply routine safety biochemistry, recommended for rituximab in clinical use.

Also all subjects will be asked if they have received standard vaccinations and if they have had chicken pox, i.e. immunity to Varicella zoster (positive antibodies if unknown). If not then vaccinations must precede the treatment with rituximab.

Tests in blood and cerebrospinal fluid (CSF)

Blood and CSF will be drawn at baseline (before intervention), and at week 20 (after intervention). Analyses will include:

Blood only

At baseline, week 20 and week 40:

- Routine clinical tests for basic haematology, 5-partsdiff including neutrophil and lymphocyte count to be able to make the neutrophil/lymphocyte ratio and platelet counts, glucose, infection, liver function, renal function, electrolyte balance, thyroid status, 25-OH-vitamin D, PTH, vitamin B12, folat
- Expression levels of selected pro-inflammatory genes (e.g. IL-1 β , caspase, IL-6, IL-8), analysed using real-time PCR and DNA microarray technology

At baseline and week 20:

- Biomarkers for gut permeability (e.g. I-FABP, GLP-2)

At baseline, week 5, 12, 20, and 40:

- B-cell populations monitoring, by flow cytometric phenotyping (e.g. CD19, CD24, CD27, CD38, CD5), to quantify the impact of rituximab treatment (*if not normalized in week 40 a repeated test will be made in week 52*)

Routine clinical tests for 5-partsdiff including neutrophil and lymphocyte count to be able to make the neutrophil/lymphocyte ratio and platelet counts. *Only at prescreening/baseline:*

- Serology for hepatitis B, C and HIV
- QuantiFERON test (interferon- γ release assay) to check for response to *Mycobacterium tuberculosis*
- Drug concentration of psychotropic medication
- Assessment of autoimmune reactions against cerebral antigens (whole blood sample, stored in – 80° C) (application of novel findings from our group)
- T cell activation against selected, recombinantly produced, human, cerebral peptides, using the method FluoroSpot, where different cytokines will act as markers for T-cell activation (PBMC sample, stored in – 80° C) (application of novel findings from our group)
- Genetic analysis for identification of predisposing factors and possible outcome predictors (e.g. polygenic risk scores and single nucleotide polymorphisms (SNPs), related to relevant psychiatric disorders) by DNA microarray technology

Blood and CSF

At baseline, week 12 (blood only), 20 (blood and CSF) and week 40 (blood only):

- Inflammatory markers (e.g. IL-6, IL-1Ra, sTNFR1) and chemokines (e.g. CCL2, CXCL13), and other immune markers (e.g. sCD14, IL-10, complement C3 and C4), measured by means of electrochemiluminescence immunoassay (Mesoscale instrument), hsCRP, Neuronal damage assessment by measuring neuron specific enolase (NSE), S100, neurofilament light chain (NFL), and neurotrophic substances (brain-derived neurotrophic factor (BDNF) and glial cell line-derived neurotrophic factor (GDNF))
- Metabolomics, to explore molecular target mechanisms

Only at baseline:

- Titres of CNS-relevant autoantibodies (e.g. anti-NMDA receptor antibodies, voltage-gated calcium channel (VGCC) antibodies, transglutaminase antibodies, anti-nuclear antibodies (ANA))

CSF only

At baseline and at week 20:

- Routine tests for CSF (e.g. cell count, albumin and immunoglobulin quotients, oligoclonal bands)
- (If sufficient number of CSF cells are available): Expression levels of pro-inflammatory genes (e.g. IL-1 β , caspase, IL-6, IL-8), analysed using real-time PCR and DNA microarray technology

Microbiology

Only at baseline:

- Routine test for presence of group A streptococci infection

Faeces

At baseline and at week 20:

Faecal samples will be collected at baseline (before intervention), and week 20 (after intervention). Patients will collect two spot samples of faeces in plastic containers at home at each time point. Analyses will include:

- F-calprotectin
- Metabolome
- Microbiome; Faecal sample for quantitative and qualitative analyses of faecal microbial composition by 16S rRNA-based next generation sequencing (NGS).

Urine

Only at baseline and week 20:

Urine samples will be collected at baseline (before interventions), and week 20 (after intervention) in parallel with collection of blood. Urine will be used for:

- Screening for pregnancy prior to the rituximab treatment (week 0)
- Illicit drug screen (baseline and week 20)

At baseline and week 20:

- 30 ml of urine, early morning sample, for assessment inflammatory markers, similar to those in blood

Brain

At baseline and week 20:

- fMRI for assessment of altered activity and extra cellular water, which may be a sign of inflammation

